### 9.6.4 Safety and Tolerability Analyses

All safety endpoints will be summarized using descriptive statistics.

The number and percentage of subjects reporting at least 1 TEAE, SAE, AESI and TEAE resulting in premature discontinuation of fipaxalparant (HZN-825) for each unique System Organ Class and Preferred Term will be summarized. AE rates (events per patient-year of follow-up during dosing) will also be summarized to account for the different treatment durations. TEAEs and SAEs will also be summarized by severity and relationship to fipaxalparant (HZN-825), as assessed by the Investigator. Grade 3 and above TEAEs will also be summarized for each unique System Organ Class and Preferred Term. AESIs will be summarized.

The number and percentage of subjects using concomitant medications will be summarized by Anatomical Therapeutic Chemical Level 4 term and Preferred Term.

Laboratory values and change from Trial Baseline and fipaxalparant (HZN-825) Baseline will be summarized by visit using descriptive statistics. The laboratory assessment will be categorized as low, normal or high based on normal ranges. Shift tables using categories of low, normal and high from each Baseline to each visit in the open-label extension will be summarized. If toxicity grading is available, then those grades will also be used for shift table summaries.

Descriptive summaries of observed and change from Trial Baseline and fipaxalparant (HZN-825) Baseline will be presented for each vital sign parameter by visit. A shift table for vital signs by toxicity grade and visit will be summarized.

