**Duration of Treatment and Follow-up:**

The duration of the Treatment Period is 52 weeks. Subjects will participate in a Safety Follow-up Visit 4 weeks after the last dose of fipaxalparant (HZN-825).

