16. Blood samples will be collected for serum and plasma biomarkers prior to dosing on Day [REDACTED] as well as at the [REDACTED] Visit.
17. Adverse events occurring or worsening after the first dose of fipaxalparant (HZN-825) on Day 1 through the Safety Follow-up Visit will be considered treatment-emergent adverse events for this trial. All adverse events that occur from the signing of informed consent through the Safety Follow-up Visit will be recorded. The subject should be assessed for the development of new onset of scleroderma renal crisis, new onset of left ventricular failure, new onset of pulmonary arterial hypertension or right heart catheterization requiring treatment, gastrointestinal dysmotility requiring enteral (tube feeding) or parenteral nutrition or digital ischemia with gangrene, amputation or hospitalization requiring treatment.
18. Includes recording of herb/supplement use. See [Table 9.1](#) for restrictions regarding medications.

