#### **9.5.3.1.2 Documentation of Adverse Events**

AEs that are ongoing at the completion of HZNP-HZN-825-301 and/or occur prior to dosing on Day 1 will be considered pre-dose AEs. The TEAE reporting period begins with administration of the first dose of fipaxalparant (HZN-825) in this extension trial on Day 1 and continues until 4 weeks after the last dose of fipaxalparant (HZN-825) or premature discontinuation. All pre-dose AEs, TEAEs and AEs during the Follow-up Period must be recorded in the source documents and on the subject's eCRF. If a subject discontinues due to an SAE, that subject will be followed per Section [9.5.3.1.5](#).

If the Investigator observes an SAE after trial completion that he/she believes was possibly caused by fipaxalparant (HZN-825), the Investigator will report this SAE using the procedures described in Section [9.5.3.1.5](#). The Investigator is responsible for collecting and documenting the outcome of AEs/SAEs.

If specifically requested, the Investigator may need to provide additional follow-up information, such as discharge summaries, medical records, or extracts from the medical records. In this case, all subject identifiers, except for the subject number, will be blinded on the copies of the medical records before submission to the Sponsor.

Detailed information regarding all SAEs must also be recorded on the Serious Adverse Event Reporting Form. Whenever clinically appropriate, the Investigator should group together into a single term the signs and symptoms that constitute a single diagnosis. For example, cough, rhinitis and sneezing might be grouped together as “upper respiratory infection” if the Investigator is confident of the diagnosis.

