**2 List of Abbreviations**

Abbreviation	Definition
ACR-CRISS	American College of Rheumatology-Composite Response Index in Systemic Sclerosis
AE	adverse events
AESI	adverse event of special interest
ANCOVA	analysis of covariance
ATC	Anatomical Therapeutic Chemical
BID	twice daily
COVID-19	Coronavirus disease of 2019
CS	clinically significant
CSR	clinical study report
CV%	coefficient of variation
DBL	database lock
DLCO	diffusing capacity of the lungs for carbon monoxide
DRM	data review meeting
EAIR	event adjusted incidence rate
ECG	electrocardiogram
eCRF	electronic case report form
EDC	electronic data capture
ESR	erythrocyte sedimentation rate
FAS	full analysis set
FACIT-F	Functional Assessment of Chronic Illness Therapy – Fatigue Scale
FCS	fully conditional specification
FVC %	forced vial capacity percent
GIT	gastrointestinal tract
HAQ-DI	Health Assessment Questionnaire - Disability Index
HRCT	high-resolution computed tomography
hsCRP	high sensitivity C-reactive Protein
ICE	intercurrent event
ICH	International Council for Harmonization of Technical Requirements for Pharmaceuticals for Human Use
ID	identification
IDMC	independent data monitoring committee
ILD	interstitial lung disease
IVRS	interactive voice response system

Abbreviation	Definition
LPAR1	lysophosphatidic acid receptor 1
ITT	intention-to-treat
LS	least squares
MAR	missing at random
MCS	mental component score
MDGA	Physician Global Assessment
MedDRA	Medical Dictionary for Regulatory Activities
mmHg	millimeters of mercury
MMRM	mixed model repeated measures
mRSS	modified Rodnan skin score
NCS	not clinically significant
PAH	pulmonary hypertension
PCS	physical component score
PD	protocol deviation
PK	pharmacokinetics
PMM	pattern mixture model
PP	per-protocol
PT	preferred term
PTGA	Patient Global Assessment
PYE	person years of exposure
Q1	first quartile
Q3	third quartile
QD	once daily
RCTC	rheumatology common toxicity criteria
SAE	serious adverse event
SAP	statistical analysis plan
SAS	statistical analysis software
SD	standard deviation
SF-12	SF-12® Health Survey
SHAQ	Scleroderma Health Assessment Questionnaire
SI	International System of Units
SMQ	standard MedDRA query
SOC	system organ class
SSc	systemic sclerosis

Abbreviation	Definition
SSC GIT	scleroderma gastrointestinal tract
SScQoL	Systemic Sclerosis Quality of Life Questionnaire
SSPRO-18	scleroderma skin patient-reported outcome
TEAE	treatment-emergent adverse event
TFL	table, figure, and listing

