## **10.3 Adverse Events**

### **10.3.1 Treatment-Emergent Adverse Events.**

Treatment-emergent adverse events (TEAEs) are defined as any AEs with an onset date on or after the trial drug start date and time (if known) and no later than 28 days after permanent discontinuation of trial drug.

Refer to the table, listing, and figure shell document for determination of TEAE status in adverse events that are missing critical AE date start and stop information. All TEAEs will be evaluated for both treatment periods (start from first dose at HZNP-HZN-825-301 and HZNP-HZN-825-302 to the end of HZNP-HZN-825-302). Imputed dates are only used for classification of TEAEs.

Prior AEs are defined as any AE with a start date prior to the date of first dose of study treatment. Prior AEs will not be summarized, but will be included in listings.

Follow-up AEs are defined as any AE occurring > 28 days after permanent discontinuation of trial drug for subjects who prematurely discontinue the study medication prior to 52 weeks (i.e. 392 days after first trial drug intake). Follow-up AEs will be identified in the listings as such. Related SAEs will be followed up until resolved or until the event stabilizes and the overall clinical outcome has been ascertained.

The Verbatim terms in the eCRFs will be mapped to preferred terms (PTs) and system organ classes (SOCs) using the current version of MedDRA. Adverse events will be graded for

severity using the Rheumatology Common Toxicity Criteria (RCTC) v2.0 [[Woodworth et al., 2007](#)].

For summaries by SOC, PT, and maximum severity, a subject will only be counted once for each SOC based on the maximum severity level reported for that SOC and once for each unique PT within that SOC level at the maximum intensity level reported for that PT.

For summaries by SOC and PT only, a subject will be counted at most once at the SOC level and at most once at each unique PT within the SOC level. Summaries presenting the frequency of TEAEs by SOC and PT will be ordered alphabetically by SOC and then, within a SOC, alphabetically by PT.

Event Adjusted Incidence Rate (EAIR) is defined as number of subjects with events / total subject-years. Subject-years for each subject will be calculated as (date of first event occurred – first dose date +1)/365.25. For subjects without an event, subject-years for each subject = (last day in study – first dose date +1)/365.25.

EAIR will be summarized by SOC and PT as needed for TEAE.

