Events for which the investigator did not record relationship to trial drug will be considered related to trial drug for summary purposes. However, by-subject data listings will show the relationship as missing. No imputation will be done in case of missing study treatment relationship for non-treatment emergent AEs.

The severity grade of events for which the investigator did not record severity will be categorized as “missing” for tabular summaries and data listings. The missing category will be listed last in summary presentation.

Treatment-emergent AEs will be summarized based on the Safety Analysis Set.

Summaries of the following types will be presented:

The number and percentage of subjects who experienced at least 1 TEAE will be provided and summarized by SOC, PT, and treatment group.

The following AEs summaries will be provided by SOC, PT, and treatment group. AE summaries followed by an asterisk(\*) will include the number of events and the corresponding incidence of events per PYE.:

- All TEAEs by maximum severity
- All treatment-emergent SAEs\*
- All treatment-related TEAEs\*
- All treatment-related TEAEs by maximum severity
- All treatment-related treatment-emergent SAEs
- All TEAEs meeting CRISS criteria
- All TEAEs leading to permanent withdrawal of any trial drug
- All TEAEs leading to death (ie, outcome of death)
- All follow-up adverse events
- All serious follow-up adverse events
- Subject incidence of AESIs: [REDACTED]

A brief, high-level summary of AEs described above will be provided by treatment group for the study treatment period and by the number and percentage of subjects who experienced the above AEs. All deaths observed in the trial will also be included in this summary. For the overall summary, the category of “TEAEs by maximum severity” described above will be replaced by AEs with severity > Grade 3.

The frequency of TEAEs occurring in > 5% of subjects in any treatment group will be summarized by treatment, primary SOC, and preferred term. A similar summary will be created for serious TEAEs occurring in > 3% of subjects in any treatment group by primary SOC and preferred term.

An adverse event plot will be created with AE incidences and risk differences (with corresponding exact 95% confidence interval) plotted together for the adverse events occurring in >5% of subjects in any treatment group. A similar plot will be created for SAEs occurring in > 3% of subjects in any treatment group.

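### The starred AE rates count events to 28 days after the last dose, but their denominator, as far as the documents define it, stops at the last dose

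*Protocol*

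**What the plan says.** **Denominator.** Protocol 9.6.4 specifies "AE rates (events per patient-year of follow-up during dosing) will also be summarized to account for the different treatment durations". In SAP 10.3.1, the AE summaries marked with an asterisk "will include the number of events and the corresponding incidence of events per PYE". Two carry the asterisk: treatment-emergent SAEs and treatment-related TEAEs. PYE is expanded only in the SAP abbreviation list, as "person years of exposure", and is given no formula. SAP 10.1 defines duration of exposure as last day of study medication minus first day, plus 1.

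**Numerator.** In SAP 10.3.1 a TEAE has its onset on or after the start of trial drug and "no later than 28 days after permanent discontinuation of trial drug". In Protocol 9.5.3.1.2 the TEAE period "continues until 4 weeks after the last dose of fipaxalparant (HZN-825) or premature discontinuation". A footnote to the schedule in Protocol 2.1 says that events "through the Safety Follow-up Visit will be considered treatment-emergent adverse events for this trial", and that visit has a window of ±14 days.

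**Periods.** "The duration of the Treatment Period is 52 weeks" in this trial. SAP 10.3.1 evaluates TEAEs over two periods: from the first dose in 302, and from the first dose in 301, each to the end of 302.

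**A different rate.** SAP 10.3.1 also says: "Event Adjusted Incidence Rate (EAIR) is defined as number of subjects with events / total subject-years". Its subject-years run to the first event or, if there is none, to the last day in study.

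**The concern.** A rate per unit of time is interpretable when events can enter the numerator only during time that is in the denominator. Here the 28 days after the last dose can add events, but if PYE means dosing time they add no patient-time. The result is neither an on-drug rate nor a rate over the treatment-emergent window.

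The protocol offers the rate as a way to allow for unequal treatment durations. A fixed 28-day tail weighs more heavily the shorter the dosing, so some dependence on duration comes back. Safety is a primary objective (Protocol 8.1), and these rates are to be tabulated by prior-treatment group. The main exposure is therefore a modest overstatement of the absolute SAE and related-TEAE rates. A smaller issue is the comparison between groups that stop early to different degrees.

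**Working it through.** The documents state no AE rate, so there is no planned figure to reproduce. What can be checked is the ratio of the rate as apparently planned to the on-drug rate.

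**Inputs from the documents**
- Dosing in 302: 52 weeks = 364 days.
- Post-dose counting window: 28 days. 364 + 28 = 392 days, the figure SAP 10.3.1 itself uses.
- Dosing across 301 and 302: 364 + 364 = 728 days.

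**Assumptions, not in the documents**
- k, the post-dose event rate divided by the on-drug rate: 0 to 1.
- Share stopping early: 5% to 40%, with a mean of 4 to 26 weeks on drug among those who stop.
- PYE follows SAP 10.1.

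**Formula.** For a subject dosed d days, ratio = (d + 28k)/d = 1 + 28k/d. For a pooled rate, d is replaced by the mean dosing time.

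**Completers**
- 302 period, k = 1: 392/364 = 1.077. With k = 0.5: 1.038. With k = 0: 1.00.
- 301 + 302 period, k = 1: 1 + 28/728 = 1.038.
- If the schedule footnote governed and the follow-up visit fell at 6 weeks: 58/52 = 1.115.

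**Single subjects who stop early, k = 1**

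| Days on drug | Ratio |
|---|---|
| 182 | 210/182 = 1.15 |
| 84 | 112/84 = 1.33 |
| 28 | 56/28 = 2.0 |
| 14 | 42/14 = 3.0 |
| 7 | 35/7 = 5.0 |

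**Pooled rate, 302 period, k = 1**
- 5% stop, mean 26 weeks: mean dosing 0.95 × 52 + 0.05 × 26 = 50.7 weeks; 1 + 4/50.7 = 1.079.
- 40% stop, mean 4 weeks: 0.60 × 52 + 0.40 × 4 = 32.8 weeks; 1 + 4/32.8 = 1.122.

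**Between groups, k = 1, all early stops at Day 84**
- 10% stop: mean 0.9 × 364 + 0.1 × 84 = 336 days; 1 + 28/336 = 1.083.
- 30% stop: mean 0.7 × 364 + 0.3 × 84 = 280 days; 1 + 28/280 = 1.100.
- Distortion of the group ratio: 1.100/1.083 = 1.015, or about 1.5%.

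**With matched windows.** Dividing events to last dose + 28 days by dosing time + 28 days gives a ratio of 1.00 at k = 1, whatever the value of d.

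**The case against.** The strongest reply is that neither document writes the mismatch down in full. Protocol 9.6.4 limits the denominator to dosing but does not state the window for the events, and its wording could be read as limiting both. The SAP states the event window but not how PYE is calculated, and it never says that PYE comes from 10.1. This stands, and it is why the finding is conditional. It does not remove the problem. The starred SAP summaries are explicitly of treatment-emergent events, and 10.1 offers the only exposure definition available to a programmer.

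The size also depends on an unstated post-dose rate. For treatment-related events in particular, an undiminished rate off drug is not secure. That too stands: the 7.7% for a completer is the top of a 0% to 7.7% range, and any k above 0 gives some inflation.

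Three stronger readings are tempting, and the documents do not support them:
- **Rates up to double.** The factor of 2.0 belongs to one subject dosed for 28 days. It is not a bound, since shorter dosing gives more, and no planned table reports it, because the reported rates are pooled.
- **A material bias between groups.** All groups take the same open-label regimen with the same counting window, so most of the inflation is common. The example leaves about 1.5%.
- **All AE rates affected.** In the SAP only two summaries use events per PYE. The EAIR counts subjects and runs to first event or last day in study. It is a separate statistic, and correcting its person-time would leave events per PYE unchanged.

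**Conclusion.** The point holds in a limited form. If PYE follows SAP 10.1, as the protocol's reference to dosing time suggests, the events-per-PYE rates for treatment-emergent SAEs and treatment-related TEAEs include post-dose events without post-dose time. As on-drug rates they are then too high by up to 7.7% for a 302 completer, and by up to about 3.8% over a full 301 + 302 period. Pooled inflation in the 302 period is about 8% to 12%. That last range assumes both an unchanged event rate for 28 days after dosing and the discontinuation pattern set out in the working. If PYE was intended to mean something else, the SAP still has to say so.

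Severity is minor to moderate. The safety analyses are descriptive, and the plan attaches no threshold or decision to these rates.

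**What to change.** In SAP 10.3.1, define PYE for the starred summaries as time from first dose to the earlier of last dose + 28 days and last contact, divided by 365.25. Derive it separately for the period starting in 301 and the period starting in 302. Reword Protocol 9.6.4 to give the same event window and person-time. State one end to the TEAE window as well, since the schedule footnote ties it to a visit that may fall up to two weeks after the 4-week mark.

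A supplementary on-drug rate, with events and time both limited to first through last dose, may be added. It should not replace the main rate, because the primary safety objective in Protocol 8.1 extends to 4 weeks after the last dose and such a rate drops post-dose events.

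The cost is a short SAP definition, one derived variable per period and a wording change in the protocol. Reported rates fall slightly. If few events occur after dosing, the matched rate will sit below the on-drug rate, at the extreme by 364/392 = 0.929 for a completer, so the table footnote should name the window.

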### **9.6.5 Pharmacokinetic Analyses**

PK data will be analyzed using the PK analysis set. Plasma concentrations of fipaxalparant (HZN-825) and metabolite(s) (if applicable) will be summarized descriptively, including arithmetic means, standard deviations, geometric means, coefficients of variation, medians, first and third quartiles and ranges, by treatment group in HZNP-HZN-825-301 and by time point. Population PK analysis may be performed.

### **9.6.6 Autoantibody Analyses**

The presence of anti-centromere antibody, anti-RNA polymerase antibody, anti-topoisomerase 1 and anti-U1 small nuclear ribonucleoprotein will be evaluated.

### **9.6.7 Interim Analyses**

No interim analyses are planned.

### **9.6.8 Sample Size and Power Considerations**

The sample size is based on the number of subjects who completed Trial HZNP-HZN-825-301.

## **9.7 Changes in the Conduct of the Trial**

If any modifications in the experimental design, dosages, parameters, subject selection or any other sections of the protocol are indicated or required, the Investigator will consult with the Sponsor before any such changes are instituted. Modifications will be accomplished through formal amendments to this protocol by the Sponsor and approved from the appropriate IRB/IEC.

The Investigator or other health professional in attendance must contact the Sponsor as soon as possible. All protocol deviations and the reasons for such deviations **must** be documented into the electronic database. In the event of a protocol deviation, the Investigator and Sponsor's Medical Monitor will determine whether the subject should continue to participate in the trial.

The Sponsor has a legal responsibility to report fully to regulatory authorities all results of administration of investigational drugs to humans. No investigational procedures other than those described in this protocol will be undertaken on the enrolled subjects without the agreement of the IRB/IEC and Sponsor.

## 10 SOURCE DOCUMENTATION AND INVESTIGATOR FILES

The Investigator must maintain adequate and accurate records to document fully the conduct of the trial and to ensure that trial data can be subsequently verified. These documents should be classified in 2 separate categories: (1) Investigator trial file and (2) subject clinical source documents that corroborate data collected in the eCRFs. Subject clinical source documents would include, as applicable, original hospital/clinic subject records; physicians' and nurses' notes; appointment book; original laboratory, ECG, echocardiogram, electroencephalogram, radiology, pathology and special assessment reports; dispensing records; signed ICFs; consultant letters; and subject enrollment logs.

In order to comply with regulatory requirements, it is the policy of the Sponsor that, at a minimum, the following be documented in source documents at the trial center:

- Medical history/physical condition and diagnosis of the subject before involvement in the trial sufficient to verify that the subject meets protocol entry criteria.
- Trial number, assigned subject number and verification that written informed consent was obtained (each recorded in dated and signed progress notes).
- Progress notes for each subject visit (each dated and signed).
- Records of each trial visit, including each trial assessment and the identity of the staff member performing the assessment.
- Trial drug dispensing and return.
- Review by the Investigator or qualified personnel on the 1572 of laboratory test results.
- AEs (start and stop date, description, relationship to trial drug, action taken and resolution).
- Investigator or Sub-Investigator's signed assessment of each AE.
- Concomitant medications (start and stop dates, reason for use).
- Condition of subject upon completion of, or premature discontinuation from, the trial.

## 11 CASE REPORT FORMS

An eCRF is required for every subject who signs the ICF. Required data must be entered on the eCRF within the required time period, which will be outlined within each site agreement, after data collection or the availability of test results. Separate source records are required to support all eCRF entries.

The Investigator will ensure that the eCRFs are accurate, complete, legible and timely and will review and provide an electronic signature for the eCRF according to the standard operating procedure of the Data Management System. Final eCRFs will be provided to the Investigator and Sponsor by Data Management.

